7 MEASUREMENTS OF TREATMENT COMPLIANCE

Not applicable. The number of infusions will be recorded as detailed in Section 10.1.

8 EFFICACY ANALYSES

All efficacy variables will be listed for all participants by treatment group and visit, and analyses performed using the RS unless specified otherwise

8.1 Statistical analysis of the primary efficacy endpoint

8.1.1 Primary analysis of the primary efficacy endpoint

The primary efficacy endpoint will be analyzed according to the following estimands' attributes:

- (1) Treatment conditions: Placebo and rozanolixizumab (please refer to section 6 Study treatments in the protocol for details)
- (2) Population: Adult Study Participants with Persistent or Chronic Primary Immune Thrombocytopenia (ITP) who fulfill the inclusion / exclusion criteria according to the protocol.
- (3) Endpoint: Durable Clinically Meaningful Platelet Response of $\geq 50 \times 10^9/L$, for at least 8 out of 12 weeks during the last 12 weeks (Week 13 to Week 25)
This endpoint includes the platelet count recorded at Week 14 to Week 25 corresponding to the response achieved following dosing at Week 13 to Week 24)
- (4) Intercurrent Events: see below.

Table 8-1: Intercurrent Events (ICE), Intercurrent Events Strategies (ICES) and Missing data Strategies for the analysis of the primary endpoint

Intercurrent Events (ICE)	ICE Strategy	Missing data strategy
a) Use of Rescue therapy from Baseline prior Week 25	A composite strategy Participants impacted by any ICE (a, b, c and d) will be considered as non-responders after the time of event.	Not applicable Section 4.2.2
b) Participants who experience any TEAEs leading to permanent treatment discontinuation		
c) Participants who discontinue prior to receiving IMP		
d) Participants who do not have any post-treatment assessment		
e) COVID-19*	A composite strategy Participants impacted by ICE (e) will be considered as non-responders at the time of event.	

* COVID-19 Impact category: Temporary discontinuation of study drug, Permanent discontinuation of study drug, Termination of study participation and Relationship to COVID-19: confirmed, suspected, general or other as recorded in the COVID-19 impact eCRF form.

(5) Population-level summary: Owing to early termination of the study, the population-level summary will be provided using descriptive statistics.

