9.3 Planned efficacy/outcome analyses

9.3.1 Analysis of the primary efficacy/primary endpoint

The primary efficacy variable is the durable clinically meaningful platelet response $\geq 50 \times 10^9/L$, for at least 8 out of 12 weeks during the last 12 weeks (platelet count recorded at Week 14 to Week 25 corresponding to the response achieved following dosing at Week 13 to Week 24). Missing platelet count at any visit will be considered "worst case" and set to zero ("no platelet response") for that specific visit.

The primary and supportive analyses for the durable platelet count endpoint are detailed in [Table 9-1](#). The main intercurrent events are rescue therapy prior to Week 25 and treatment discontinuation (withdrawal from study) due to TEAEs.

Confirmatory testing of single hypotheses is based on a closed-testing procedure.

The primary analysis of the study will use a Stratified Cochran-Mantel-Haenszel test statistic.

This document cannot be used to support any marketing authorization application and any extensions or variations thereof.

PUBLIC COPY

Table 9-1: Estimands for the primary endpoint

Estimand					
Objective Clinical Category	Statistical Category	Variable/Endpoint	Population	IES^a	PLS^b (Analysis)
Primary Objective: To demonstrate clinical efficacy of rozanolixizumab as a maintenance treatment in participants with primary ITP					
Platelet Count	Primary/MCP	Durable Clinically Meaningful Platelet Response of $\geq 50 \times 10^9/L$, for at least 8 out of 12 weeks during the last 12 weeks (Week 13 to Week 25)	RS who were randomized to rozanolixizumab weekly dosing compared against those who received placebo.	A composite strategy will be used, in which participants who require rescue therapy, who experience any TEAEs leading to treatment discontinuation, discontinue prior to receiving IMP, or do not have a post-treatment assessment will be considered as nonresponders.	To test of the null hypothesis (H_0) in participants who have achieved a durable platelet count that the true common odds ratio between treatment arms is 1 (odds ratio = 1) vs the alternative hypothesis (H_a) that the odds ratio is less than 1, a Cochran-Mantel-Haenszel model adjusted for the stratification factors, namely baseline degree of thrombocytopenia (platelet count $<$ or $\geq 15 \times 10^9/L$), history of splenectomy (yes or no).

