2.4 Determination of sample size

Following Protocol Amendment 3, the sample size calculation was amended to reflect the primary objective of assessing the treatment effect on participants who were randomized to weekly infusions. To achieve the study objectives within the sample size cap of the original 2-stage adaptive design, the futility assessment and option for a sample size re-assessment were no longer considered and the sample size calculation was amended as appropriate for a fixed parallel group design.

The observed durable platelet response rates (platelet count $\geq 50 \times 10^9/L$ during 6 or more of the last 8 weeks of treatment), from Kuter et al (2008) in splenectomized participants were 38% (16/42) on active and 0% (0/21) on placebo. In non-splenectomized participants the rates were 61% (25/41) and 5% (1/21), respectively.

Using the true response rate of 0.45 versus 0.05, a sample size of 60 participants randomized in a 2:1 ratio (ie, $n=40$ on rozanolixizumab and $n=20$ on placebo) receiving weekly infusions would provide >90% power to detect a statistically significant difference between treatment groups using Fisher's Exact Test at an alpha level of 0.025 (1-sided).

By definition participants who dropout of the study are determined as nonresponders and are incorporated in the overall response rate. If the number of dropouts is greater than anticipated by 10%, the impact on the rozanolixizumab response rate would mean that it would drop to a response rate of 0.4. In such cases, the study would still achieve >80% power if the overall response rate on placebo remains at 0.05.

If the response rate on placebo was 0.1 rather than the anticipated 0.05, the rozanolixizumab rate would need to be >0.45 to achieve 80% and >0.5 to achieve 90% power. Table 2-1 provides power estimates for a fixed study design of n=60 participants in a 2:1 randomization ratio.

Table 2-1: Expected sample size

Scenario	Placebo Response Rate of 0.05			Placebo Response Rate of 0.1		
	RLZ	Placebo	Power ^a	RLZ	Placebo	Power ^a
1	0.30	0.05	56%	0.30	0.10	32%
2	0.35	0.05	73%	0.35	0.10	48%
3	0.40	0.05	85%	0.40	0.10	63%
4	0.45	0.05	93%	0.45	0.10	77%
5	0.50	0.05	97%	0.50	0.10	87%
6	0.55	0.05	98%	0.55	0.10	93%

^a Power for a Parallel Group Design with N=60 in a 2:1 randomization test computed with Fisher's exact test using NQuery Advisor 7.0.

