4.2 Handling of dropouts or missing data

4.2.1 Handling missing data for the primary and secondary efficacy endpoints

Study participants who have not met the threshold for clinically meaningful response will be imputed as non-responders for the analysis. Missing platelet data at any visit will be considered "worst case" and set to zero ("no response") for that specific visit.

Missing data for ITP Patient Assessment Questionnaire (ITP PAQ) instrument will not be imputed.

Missing efficacy data encountered due to permanent treatment discontinuation due to TEAEs, or the receipt of rescue therapy will be considered as intercurrent events. For the primary efficacy analysis, patients with intercurrent events will be considered as non-responders.

Missing data strategy for PRO related endpoints will follow instructions indicated in each instrument.

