4.2.2 Missing Data due to COVID-19

Unless specified otherwise, study participants who have visits impacted by COVID-19 for any reason will be considered non-responders at the corresponding visit, and missing platelet count data due to COVID-19 will be considered worst case and set to zero ("no response") for that particular visit.

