8.2 Statistical analysis of the secondary efficacy endpoints

8.2.1 Cumulative number of weeks with Clinically Meaningful Platelet Response of $\geq 50 \times 10^9/L$ over the 24-Week treatment period (Week 1 to Week 25)

The secondary efficacy endpoint: Cumulative number of weeks with Clinically Meaningful Platelet Response of $\geq 50 \times 10^9/L$ over the 24-week treatment period will be analyzed on the RS, under the same treatment conditions and population of interest as for the primary endpoint. Note: if platelet count was assessed multiple times in a given week, Clinically Meaningful Platelet Response only needed to be observed at one timepoint during the week. ICE, ICES and population level summary will be handled as described below:

Table 8-2: Intercurrent Events (ICE), Intercurrent Events Strategies (ICES) and Missing data Strategies for the analysis of the Cumulative number of weeks with Clinically Meaningful Platelet Response of $\geq 50 \times 10^9/L$ over the 24-Week treatment period

Intercurrent Events (ICE)	ICE Strategy	Missing data strategy
a) Use of rescue therapy	A while on-treatment strategy: Participants impacted by	Participants impacted by any of the ICE will be considered as having a loss
b) Withdrawal from the study due to treatment emergent AE		

Intercurrent Events (ICE)	ICE Strategy	Missing data strategy
c) Permanent treatment discontinuation	any of the ICE will be considered as having a loss of durable platelet response at the time of the ICE occurring.	of durable platelet response at the time of the ICE occurring. Platelet data up to the start date of this ICE will be utilized in statistical analysis.
d) COVID-19*	A composite strategy: data impacted by COVID-19 will be considered as having a loss of durable platelet response at the time of the ICE occurring.	Section 4.2.2

* COVID-19 Impact category: Temporary discontinuation of study drug, Permanent discontinuation of study drug, Termination of study participation and Relationship to COVID-19: confirmed, suspected, general or other as recorded in the COVID-19 impact eCRF form.

Population-level summary: Owing to early termination of the study, the population-level summary will be provided using descriptive statistics.

8.2.2 Time to first Clinically Meaningful Platelet Response of $\geq 50 \times 10^9/L$: time from starting treatment to achievement of first response of $\geq 50 \times 10^9/L$.

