8.2.2.2 Estimand's attributes

This secondary efficacy endpoint will be analyzed using the RS, under the same treatment conditions and population as for the primary endpoint while using the ICE, ICES described in Table 8-3 and the population level summary described below:

Table 8-3: Intercurrent Events (ICE), Intercurrent Events Strategies (ICES) and Missing data Strategies for the analysis of Time to first Clinically Meaningful Response of $\geq 50 \times 10^9/L$

Intercurrent Events (ICE)	ICE Strategy	Missing data strategy
a) Use of rescue therapy prior to Week 25	A while on-treatment strategy: For participants impacted by any of the ICE (a, b and c). Impacted data will be excluded from the time at risk.	Available platelet data up to the start date of this ICE will be utilized in statistical analysis.
b) Withdrawal from the study due to treatment emergent AE		
c) Permanent treatment discontinuation		
d) COVID-19*	Composite Strategy: data impacted by COVID-19 will	Section 4.2.2

Intercurrent Events (ICE)	ICE Strategy	Missing data strategy
	be excluded from the time at risk.	

* COVID-19 Impact category: Temporary discontinuation of study drug, Permanent discontinuation of study drug, Termination of study participation and Relationship to COVID-19: confirmed, suspected, general or other as recorded in the COVID-19 impact eCRF form.

Population-level summary: Owing to early termination of the study, the population-level summary will be provided using descriptive statistics. Median time to event will be estimated as median of observed values and also using the Kaplan-Meier estimate.

8.2.3 Clinically Meaningful Platelet Response by Day 8, defined as platelet count $\geq 50 \times 10^9/L$

This secondary efficacy endpoint will be analyzed using the RS, under the same treatment conditions and population as for the primary endpoint while using the ICE/ICES described in Table 8-4 and the population level summary described below:

Table 8-4: Intercurrent Events (ICE), Intercurrent Events Strategies (ICES) and Missing data Strategies for the analysis of Clinically Meaningful Response by Day 8

Intercurrent Events (ICE)	ICE Strategy	Missing data strategy
a) Use of rescue therapy up to Day 8	Composite strategy: Participants impacted by any of these ICE will be considered as non-responders.	Participants with missing data due to any of these ICE will be considered as non-responders.
b) TEAEs leading to permanent treatment discontinuation		

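### SAP Table 8-1 time-limits non-response after an intercurrent event in the primary endpoint; protocol Table 9-1 and SAP 4.2.1 do not

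*SAP*

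**What the plan says.** SAP 8.1.1 labels the handling in Table 8-1 a composite strategy. Its events are (a) rescue before Week 25, (b) a treatment-emergent adverse event that ends treatment permanently, (c) discontinuation before any dose, (d) no post-treatment assessment, and (e) COVID-19. For the first four the rule is "Participants impacted by any ICE (a, b, c and d) will be considered as non-responders after the time of event".

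Other places that govern the same endpoint carry no such time limit:

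- SAP 4.2.1: "For the primary efficacy analysis, patients with intercurrent events will be considered as non-responders".
- Protocol Table 9-1, primary row: "A composite strategy will be used, in which participants who require rescue therapy, who experience any TEAEs leading to treatment discontinuation". Together with those who stop before dosing or have no post-treatment assessment, these participants are nonresponders. The text of protocol 9.3.1 adds "The main intercurrent events are rescue therapy prior to Week 25 and treatment discontinuation (withdrawal from study) due to TEAEs", so its only time boundary is Week 25, and it is attached to rescue.
- SAP 2.4, on dropouts: "By definition participants who dropout of the study are determined as nonresponders and are incorporated in the overall response rate".

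Elsewhere in the SAP, Table 8-4 (Day 8 response, SAP 8.2.3) also uses a composite rule for its events a to d, without a time limit: "Composite strategy: Participants impacted by any of these ICE will be considered as non-responders". Table 8-6 (SAP 8.3.1) does likewise. For COVID-19, SAP 4.2.2 applies non-response by visit: "study participants who have visits impacted by COVID-19 for any reason will be considered non-responders at the corresponding visit". SAP 3.9, which lists changes to the protocol-defined analyses, records the addition of COVID-19 as an intercurrent event but says nothing about a time limit for the others.

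**The concern.** The five closing words of the Table 8-1 rule can be read in two ways. On a participant-level reading, anyone with event a to d fails the primary endpoint. On a by-visit reading, only counts after the event become non-response, and earlier counts still go towards the required 8. The protocol's composite estimand allows only the first.

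The by-visit reading is not far-fetched. The COVID-19 row of the same table is also labelled composite and also time-qualified, and SAP 4.2.2 implements it visit by visit. A programmer could treat the other rows in the same way. Protocol 6.4.3 lets rescued participants stay on study drug and asks them to complete their remaining visits, so a late rescue preceded by a run of qualifying counts can occur within the plan.

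At stake is whether a participant rescued inside the 12-week window can be counted as a durable responder. With inference dropped, the descriptive response rate is the primary efficacy result.

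**Working it through.** **The plan's own figure.** The documents give no figure on this point. The nearest is the power in SAP Table 2-1, scenario 4 (0.45 vs 0.05, 40 vs 20 participants, Fisher's exact test, one-sided 0.025): stated 93%, and full enumeration gives 93.0%. Neither reading changes it.

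**Inputs**

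- Counts entering the endpoint: Weeks 14 to 25 (SAP 8.1.1), so 25 − 14 + 1 = 12, taking one count per week. SAP 8.1.1 gives the range without saying weekly. The 12-week wording of the endpoint and the weekly counts in the protocol synopsis support it, but the analysed participants followed earlier protocol versions (SAP 3.2.1).
- Threshold: at least 8 of the 12.
- Rescue counts as an event up to, but not including, Week 25 (Table 8-1).
- Last planned dose for the analysed participants: Week 23 (SAP 2.3).
- Analysed participants: 33 (SAP 2.4).

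**When the two readings differ.** Under the by-visit reading, the largest number of responding weeks equals the number of counts from Week 14 up to the last count before the event.

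| Event follows the count at | Counts available | May be below 50×10⁹/L and still reach 8 | By-visit result possible | Participant-level result |
|---|---|---|---|---|
| Week 20 | 7 | cannot reach 8 | non-responder | non-responder |
| Week 21 | 8 | 0 | responder | non-responder |
| Week 22 | 9 | 1 | responder | non-responder |
| Week 23 | 10 | 2 | responder | non-responder |
| Week 24 | 11 | 3 | responder | non-responder |

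Only events after the Week 21 count separate the readings.

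**Width of the window.** Nominal day = 7 × (week − 1) + 1, so Week 21 = Day 141, Week 23 = Day 155 and Week 25 = Day 169. As a check on the bi-weekly schedule, Day 155 + 56 days of follow-up = Day 211, the end of follow-up given in SAP 2.3.

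- Rescue: 169 − 141 = 28 days.
- Adverse event that ends treatment: 155 − 141 = 14 days at most, since no planned dose remains after Week 23.

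Both use nominal days and ignore visit windows.

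**Which events matter.** Only a and b. For c and d there is no on-treatment or post-treatment count to preserve, so the time limit has nothing to act on. For b, counts after withdrawal will usually be missing and set to zero under SAP 4.2.1 anyway. A by-visit rule would then add almost nothing to the missing-data rule. SAP 8.1.1 also does not date event b; SAP 8.2.5 uses the start of the adverse event, but only for time to first rescue.

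**Shift per reclassified participant.** The documents give no split by arm. Taking 2:1 of 33 as 22 and 11:

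- rozanolixizumab: 1/22 = 4.5 points
- placebo: 1/11 = 9.1 points

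For assumed splits from 20/13 to 24/9, the shift runs from 1/20 = 5.0 to 1/24 = 4.2 points on rozanolixizumab, and from 1/13 = 7.7 to 1/9 = 11.1 points on placebo.

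**The case against.** The best defence is that the SAP already settles the matter at participant level. SAP 4.2.1 has a sentence specific to the primary analysis, and it classifies patients, not visits. The Table 8-1 rule also has participants as its subject. Where the SAP wants pre-event data to count, it says so: Tables 8-2 and 8-3 use a while-on-treatment label, and Table 8-2 states "Platelet data up to the start date of this ICE will be utilized in statistical analysis". Events c and d share the disputed sentence and make sense only as participant-level failure. The time limit itself has a harmless reading: durable response is determined when the window closes at Week 25, so someone who is a non-responder from the event onwards is a non-responder when status is assigned.

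Much of this stands. Participant-level failure is probably what was meant. If so, the silence of SAP 3.9 and the missing date for event b are not defects. SAP 2.4 is weak support, because it concerns dropouts in a weekly-dosing design that enrolled nobody, and rescued participants need not drop out. The scenario is also uncommon: it needs a sustained response followed by a late event, and protocol 4.3 reports that platelet counts were not sustained over the initial dosing interval in the extension study.

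This does not remove the conflict. On the participant-level reading the five words do nothing. The COVID-19 row shows that in this SAP a composite label with a time qualifier can mean by-visit handling. Neither 4.2.1 nor 8.1.1 says which prevails.

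**Conclusion.** The concern holds. The SAP gives two differently worded rules for intercurrent events in the primary endpoint. Applied by visit, the one in Table 8-1 can make a participant with rescue, or with an adverse event that ends treatment, after the Week 21 count a durable responder. That would contradict the protocol estimand and would be a change not declared in SAP 3.9.

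The practical effect is small. It is confined to a descriptive response rate in 33 participants, no test depends on it, and the by-visit efficacy listings (SAP 8) would let a reader check the derivation. The number of participants affected is not given and may be zero. The point sizes rest on assumed arm sizes, and the Week 21 cut-off rests on one count per week. The wording should still be corrected, because it defines the primary endpoint.

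**What to change.** In SAP Table 8-1, delete the last five words of the rule for events a to d. Rescue before Week 25, or an adverse event that ends treatment permanently, then makes the participant a non-responder for the whole endpoint, in line with SAP 4.2.1 and protocol Table 9-1. No event date is then needed for event b. The COVID-19 row can stay as it is.

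The cost is one table cell. Compared with by-visit programming, the reported response rate in either arm can only stay the same or fall.

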8.2 Statistical analysis of the secondary efficacy endpoints

8.2.1 Cumulative number of weeks with Clinically Meaningful Platelet Response of $\geq 50 \times 10^9/L$ over the 24-Week treatment period (Week 1 to Week 25)

The secondary efficacy endpoint: Cumulative number of weeks with Clinically Meaningful Platelet Response of $\geq 50 \times 10^9/L$ over the 24-week treatment period will be analyzed on the RS, under the same treatment conditions and population of interest as for the primary endpoint. Note: if platelet count was assessed multiple times in a given week, Clinically Meaningful Platelet Response only needed to be observed at one timepoint during the week. ICE, ICES and population level summary will be handled as described below:

Table 8-2: Intercurrent Events (ICE), Intercurrent Events Strategies (ICES) and Missing data Strategies for the analysis of the Cumulative number of weeks with Clinically Meaningful Platelet Response of $\geq 50 \times 10^9/L$ over the 24-Week treatment period

Intercurrent Events (ICE)	ICE Strategy	Missing data strategy
a) Use of rescue therapy	A while on-treatment strategy: Participants impacted by	Participants impacted by any of the ICE will be considered as having a loss
b) Withdrawal from the study due to treatment emergent AE		

Intercurrent Events (ICE)	ICE Strategy	Missing data strategy
c) Permanent treatment discontinuation	any of the ICE will be considered as having a loss of durable platelet response at the time of the ICE occurring.	of durable platelet response at the time of the ICE occurring. Platelet data up to the start date of this ICE will be utilized in statistical analysis.
d) COVID-19*	A composite strategy: data impacted by COVID-19 will be considered as having a loss of durable platelet response at the time of the ICE occurring.	Section 4.2.2

* COVID-19 Impact category: Temporary discontinuation of study drug, Permanent discontinuation of study drug, Termination of study participation and Relationship to COVID-19: confirmed, suspected, general or other as recorded in the COVID-19 impact eCRF form.

Population-level summary: Owing to early termination of the study, the population-level summary will be provided using descriptive statistics.

8.2.2 Time to first Clinically Meaningful Platelet Response of $\geq 50 \times 10^9/L$: time from starting treatment to achievement of first response of $\geq 50 \times 10^9/L$.

